Treatment-emergent adverse events are those events with an onset after the first application of E-BPO 5% Cream.

Related defined as “Definitely”, “Probably”, or “Possible”. Not Related defined as “Unlikely” or “Not related”.

SOURCE: USERNAME\SPONSOR\PROJECT\JOBNAME (DATE, TIME)

Table 14.3.1.5.1: Summary of Treatment-Emergent Serious Adverse Event Characteristics – By Period
(Safety Population)
(Page 1 of 2)

	0-12 Weeks (N=xxx)	>12-28 Weeks (N=xxx)	>28-52 Weeks (N=xxx)	>52 Weeks (N=xxx)
Subjects Reporting Any Serious Treatment-Emergent Adverse Event	xx (xx.x%)	xx (xx.x%)	xx (xx.x%)	xx (xx.x%)
Number of Serious Treatment-Emergent Adverse Events	xx	xx	xx	xx
Subjects Reporting Serious Treatment-Emergent Adverse Event with Outcome of Fatal	xx (xx.x%)	xx (xx.x%)	xx (xx.x%)	xx (xx.x%)
Number of Serious Treatment-Emergent Adverse Events with Outcome of Fatal	xx	xx	xx	xx
Subjects Who Discontinued Study Drug Due to a Serious Treatment-Emergent Adverse Event	xx (xx.x%)	xx (xx.x%)	xx (xx.x%)	xx (xx.x%)
Number of Serious Treatment-Emergent Adverse Events Leading to Discontinuation of Study Drug	xx	xx	xx	xx
Subjects Who Discontinued from the Study Due to a Serious Treatment-Emergent Adverse Event	xx (xx.x%)	xx (xx.x%)	xx (xx.x%)	xx (xx.x%)
Number of Serious Treatment-Emergent Adverse Events Leading to Discontinuation of Study	xx	xx	xx	xx

Note: Treatment-emergent adverse events are those events with an onset after the first application of E-BPO 5% Cream. Related defined as “Definitely”, “Probably”, or “Possible”. Not Related defined as “Unlikely” or “Not related”.
Periods defined from date of first dose of E-BPO 5% Cream. Period >52 Weeks includes all adverse events reported after week 52 through the end of study participation.
By subject denominator for each period includes the number of subjects in the safety population completing the period or experiencing an adverse event during the period.

SOURCE: USERNAME\SPONSOR\PROJECT\JOBNAME (DATE, TIME)

Table 14.3.1.5.1: Summary of Treatment-Emergent Serious Adverse Event Characteristics – By Period
(Safety Population)
(Page 2 of 2)

	0-12 Weeks (N=xxx)	>12-28 Weeks (N=xxx)	>28-52 Weeks (N=xxx)	>52 Weeks (N=xxx)
By Maximum Severity				
Severe	xx (xx.x%)	xx (xx.x%)	xx (xx.x%)	xx (xx.x%)
Moderate	xx (xx.x%)	xx (xx.x%)	xx (xx.x%)	xx (xx.x%)
Mild	xx (xx.x%)	xx (xx.x%)	xx (xx.x%)	xx (xx.x%)
By Strongest Relationship to Study Drug				
Related	xx (xx.x%)	xx (xx.x%)	xx (xx.x%)	xx (xx.x%)
Not Related	xx (xx.x%)	xx (xx.x%)	xx (xx.x%)	xx (xx.x%)
Maximum Severity within Relationship to Study Drug				
Related				
Severe	xx (xx.x%)	xx (xx.x%)	xx (xx.x%)	xx (xx.x%)
Moderate	xx (xx.x%)	xx (xx.x%)	xx (xx.x%)	xx (xx.x%)
Mild	xx (xx.x%)	xx (xx.x%)	xx (xx.x%)	xx (xx.x%)
Not Related				
Severe	xx (xx.x%)	xx (xx.x%)	xx (xx.x%)	xx (xx.x%)
Moderate	xx (xx.x%)	xx (xx.x%)	xx (xx.x%)	xx (xx.x%)
Mild	xx (xx.x%)	xx (xx.x%)	xx (xx.x%)	xx (xx.x%)

Note: Treatment-emergent adverse events are those events with an onset after the first application of E-BPO 5% Cream.

Related defined as “Definitely”, “Probably”, or “Possible”. Not Related defined as “Unlikely” or “Not related”.

Periods defined from date of first dose of E-BPO 5% Cream. Period >52 Weeks includes all adverse events reported after week 52 through the end of study participation.

By subject denominator for each period includes the number of subjects in the safety population completing the period or experiencing an adverse event during the period.

SOURCE: USERNAME\SPONSOR\PROJECT\JOBNAME (DATE, TIME)

Table 14.3.1.5.2: Summary of Treatment-Emergent Serious Adverse Events by MedDRA System Organ Class and Preferred Term – By Period
(Safety Population)
(Page 1 of x)

System Organ Class ^a Preferred Term	0-12 Weeks (N=xxx)	>12-28 Weeks (N=xxx)	>28-52 Weeks (N=xxx)	>52 Weeks (N=xxx)
XXXXXXXXXXXXXXXXXXXXXXXXXXXXXXXXXXXX XXXXXXXXXXXXXXXXXXXXXXXXXXXXXXXXXXXX	xx (xx.x%) xx (xx.x%)	xx (xx.x%) xx (xx.x%)	xx (xx.x%) xx (xx.x%)	xx (xx.x%) xx (xx.x%)

^a Counts reflect numbers of subjects reporting one or more adverse events that map to MedDRA. At each level of summarization (System Organ Class or Preferred Term) subjects are counted once. By subject denominator for each period includes the number of subjects in the safety population completing the period or experiencing an adverse event during the period.

Note: MedDRA Version 21.0

Treatment-emergent adverse events are those events with an onset after the first application of E-BPO 5% Cream.

Periods defined from date of first dose of E-BPO 5% Cream. Period >52 Weeks includes all adverse events reported after week 52 through the end of study participation.

SOURCE: USERNAME\SPONSOR\PROJECT\JOBNAME (DATE, TIME)

Table 14.3.1.5.3: Summary of Treatment-Emergent Serious Adverse Events by Severity – By Period
(Safety Population)
(Page 1 of x)

System Organ Class ^a Preferred Term	Severity	0-12 Weeks (N=xxx)	>12-28 Weeks (N=xxx)	>28-52 Weeks (N=xxx)	>52 Weeks (N=xxx)
XXXXXXXXXXXXXXXXXXXXXXXXXXXX	Severe	xx (xx.x%)	xx (xx.x%)	xx (xx.x%)	xx (xx.x%)
	Moderate	xx (xx.x%)	xx (xx.x%)	xx (xx.x%)	xx (xx.x%)
	Mild	xx (xx.x%)	xx (xx.x%)	xx (xx.x%)	xx (xx.x%)
XXXXXXXXXXXXXXXXXXXXXXXXXXXX	Severe	xx (xx.x%)	xx (xx.x%)	xx (xx.x%)	xx (xx.x%)
	Moderate	xx (xx.x%)	xx (xx.x%)	xx (xx.x%)	xx (xx.x%)
	Mild	xx (xx.x%)	xx (xx.x%)	xx (xx.x%)	xx (xx.x%)

^a Counts reflect numbers of subjects reporting one or more adverse events that map to MedDRA. At each level of summarization (System Organ Class or Preferred Term) subjects are counted once under the greatest reported severity. By subject denominator for each period includes the number of subjects in the safety population completing the period or experiencing an adverse event during the period.

Note: MedDRA Version 21.0

Treatment-emergent adverse events are those events with an onset after the first application of E-BPO 5% Cream.

Periods defined from date of first dose of E-BPO 5% Cream. Period >52 Weeks includes all adverse events reported after week 52 through the end of study participation.

SOURCE: USERNAME\SPONSOR\PROJECT\JOBNAME (DATE, TIME)

Table 14.3.1.5.4: Summary of Treatment-Emergent Serious Adverse Events by Relationship to Study Drug – By Period
 (Safety Population)
 (Page 1 of xx)

System Organ Class ^a Preferred Term	Relationship	0-12 Weeks	>12-28 Weeks	>28-52 Weeks	>52 Weeks
		(N=xxx)	(N=xxx)	(N=xxx)	(N=xxx)
XXXXXXXXXXXXXXXXXXXXXXXXXXXX	Related	xx (xx.x%)	xx (xx.x%)	xx (xx.x%)	xx (xx.x%)
	Not Related	xx (xx.x%)	xx (xx.x%)	xx (xx.x%)	xx (xx.x%)
XXXXXXXXXXXXXXXXXXXXXXXXXXXX	Related	xx (xx.x%)	xx (xx.x%)	xx (xx.x%)	xx (xx.x%)
	Not Related	xx (xx.x%)	xx (xx.x%)	xx (xx.x%)	xx (xx.x%)

^a Counts reflect numbers of subjects reporting one or more adverse events that map to MedDRA. At each level of summarization (System Organ Class or Preferred Term) subjects are counted once under the greatest reported relationship. By subject denominator for each period includes the number of subjects in the safety population completing the period or experiencing an adverse event during the period.

Note: MedDRA Version 21.0.

Treatment-emergent adverse events are those events with an onset after the first application of E-BPO 5% Cream.

Related defined as “Definitely”, “Probably”, or “Possible”. Not Related defined as “Unlikely” or “Not related”.

Periods defined from date of first dose of E-BPO 5% Cream. Period >52 Weeks includes all adverse events reported after week 52 through the end of study participation.

SOURCE: USERNAME\SPONSOR\PROJECT\JOBNAME (DATE, TIME)

Table 14.3.1.4.1: Summary of Vital Signs
(Safety Population)
(Page 1 of 20)

Temperature (°C)	E-BPO 5% Cream (N=xxx)
Baseline ^a	
n	xxx
Mean	xx.x
SD	xx.xx
Median	xx.x
Min. to Max.	xx to xx
Week 12 ^b	
n	xxx
Mean	xx.x
SD	xx.xx
Median	xx.x
Min. to Max.	xx to xx
Change from Baseline	
n	xxx
Mean	xx.x
SD	xx.xx
Median	xx.x
Min. to Max.	xx to xx

^a Baseline is defined as the baseline value from SGT-54-01/SGT-54-02.

^b Table summaries based analysis visits, representing time from first dose of E-BPO 5% Cream.

Note: Negative change values represent decrease from Baseline.

SOURCE: USERNAME\SPONSOR\PROJECT\JOBNAME (DATE, TIME)

Table 14.3.1.4.1: Summary of Vital Signs
(Safety Population)
(Page 2 of 20)

Temperature (°C)	E-BPO 5% Cream (N=xxx)
Week 24 ^b	
n	xxx
Mean	xx.x
SD	xx.xx
Median	xx.x
Min. to Max.	xx to xx
Change from Baseline	
n	xxx
Mean	xx.x
SD	xx.xx
Median	xx.x
Min. to Max.	xx to xx

^a Baseline is defined as the baseline value from SGT-54-01/SGT-54-02.

^b Table summaries based analysis visits, representing time from first dose of E-BPO 5% Cream.

Note: Negative change values represent decrease from Baseline.

SOURCE: USERNAME\SPONSOR\PROJECT\JOBNAME (DATE, TIME)

Table 14.3.1.4.1: Summary of Vital Signs
(Safety Population)
(Page 3 of 20)

Temperature (°C)	E-BPO 5% Cream (N=xxx)
Week 36 ^b	
n	xxx
Mean	xx.x
SD	xx.xx
Median	xx.x
Min. to Max.	xx to xx
 Change from Baseline	
n	xxx
Mean	xx.x
SD	xx.xx
Median	xx.x
Min. to Max.	xx to xx

^a Baseline is defined as the baseline value from SGT-54-01/SGT-54-02.

^b Table summaries based analysis visits, representing time from first dose of E-BPO 5% Cream.

Note: Negative change values represent decrease from Baseline.

SOURCE: USERNAME\SPONSOR\PROJECT\JOBNAME (DATE, TIME)

Table 14.3.1.4.1: Summary of Vital Signs
(Safety Population)
(Page 4 of 20)

Temperature (°C)	E-BPO 5% Cream (N=xxx)
Week 48 ^b	
n	xxx
Mean	xx.x
SD	xx.xx
Median	xx.x
Min. to Max.	xx to xx
Change from Baseline	
n	xxx
Mean	xx.x
SD	xx.xx
Median	xx.x
Min. to Max.	xx to xx

^a Baseline is defined as the baseline value from SGT-54-01/SGT-54-02.

^b Table summaries based analysis visits, representing time from first dose of E-BPO 5% Cream.

Note: Negative change values represent decrease from Baseline.

SOURCE: USERNAME\SPONSOR\PROJECT\JOBNAME (DATE, TIME)

Repeat these pages for [**Respiratory Rate (breaths/min), Systolic Blood Pressure (mmHg), Diastolic Blood Pressure (mmHg) and Heart Rate (beats/min)**]

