
Methodology:
	
Clinical and Safety Evaluations will be performed at:
 
 1. Visit 1/Screening, only applies for new patients 2. Visit 2/Baseline, Day 1 can also be Visit 6/Week 12, Day 85 of Study SGT-54-01 or Study SGT-54-02 3. Visit 3/Week 4, Day 29 (\pm 10 Days) 4. Visit 4/Week 8, Day 57 (\pm 10 Days) 5. Visit 5/Week 12, Day 85 (\pm 10 Days) 6. Visit 6/Week 16, Day 113 (\pm 10 Days) 7. Visit 7/Week 20, Day 141 (\pm 10 Days) 8. Visit 8/Week 24, Day 169 (\pm 10 Days) 9. Visit 9/Week 28, Day 197 (\pm 10 Days) 10. Visit 10/Week 32, Day 225 (\pm 10 Days) 11. Visit 11/Week 36, Day 253 (\pm 10 Days) 12. Visit 12/Week 40, Day 281 (\pm 10 Days)/ End of Treatment/End of Study for patients who complete the study, early terminate, or if the Sponsor terminates the study prematurely (only for patients that completed Study SGT-54-01 or Study SGT-54-02) 
Applies for new patients:
 
 13. Visit 13/Week 44, Day 309 (\pm 10 Days) 14. Visit 14/Week 48, Day 337 (\pm 10 Days) 15. Visit 15/Week 52, Day 365 (+ 10 Days)/ End of Treatment/End of Study for patients who complete the study, early terminate, or if the Sponsor terminates the study prematurely. 
Patients will be admitted into the study only if they completed Study SGT-54-01 or Study SGT-54-02 at Week 12 within the window time or missed no more than one study Visit 3, 4 or 5 in these studies. For patients that were enrolled for study SGT-54-01 or study SGT-54-02 clinical exclusion criteria (IGA grade or lesion count) will not limit the enrollment for the study. New patients who meet specified inclusion criteria (including moderate to severe rosacea according to 5-point IGA scale and have a minimum total of 15 and a maximum total of 70 inflammatory lesions (papules and/or pustules) including those present on the nose) and none of the exclusion criteria will be admitted to the study.
 
At each visit a 5-point IGA scale of rosacea; rosacea erythema, and telangiectasia; will be performed and recorded. If a patient is assessed as “mild”, “moderate” or “severe” (2, 3 or 4 respectively), study product will be dispensed and the patient will use the study product daily according to patient instructions. If a patient is assessed as “clear” (0) or “almost clear” (1), the patient will not be dispensed the study product.
 
In addition, at each visit, the following safety measures will be recorded: monitoring for any AE including local and systemic; investigator Cutaneous Safety Assessment rating of erythema, dryness and scaling and

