14. CLINICAL OUTCOME ASSESSMENTS

14.1. Investigator Global Assessment (IGA)

The IGA will be performed at all study visits.

If a patient is assessed as “clear” (0) or “almost clear” (1), the patient will not be dispensed the study product. If a patient is assessed as “mild”, “moderate” or “severe” (2, 3 or 4, respectively), study product will be dispensed and the patient will use the study product daily according to patient instructions.

In the event a subject is not dispensed IP at a given visit due to an IGA of "clear" or "almost clear," and the subject's rosacea condition worsens, an unscheduled visit can be performed for assessing the subject and dispensing IP, if appropriate.

The IGA scale provided in [Table 1](#) will be used to describe the severity grade and subsequent score:

Table 1: Investigator Global Assessment (IGA) Scale

Grade	Description
0 – Clear	Skin clear of inflammatory papules or pustules
1 – Almost Clear	Very few small papules or pustules and very mild dull erythema is present
2 – Mild	Few small papules or pustules and mild dull or light pink erythema is present
3 – Moderate	Several to many small or larger papules or pustules and moderate light to bright red erythema is present
4 – Severe	Numerous small and/or larger papules or pustules and severe erythema that is bright red to deep red is present

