17.4. Preparation, Dispensing and Storage Instructions

The study product must be dispensed only to study patients and only at study sites specified on the form FDA 1572 by authorized personnel as required by applicable regulations and guidelines.

Study product will be dispensed according to Investigator Global Assessment at: Baseline, Weeks 4, 8, 12, 16, 20, 24, 28, 32 and 36 for patients entering from study SGT-54-01 or study SGT-54-02 and for new patients at: Baseline, Weeks 4, 8, 12, 16, 20, 24, 28, 32, 36, 40, 44 and 48. Study product will be returned at: Weeks 4, 8, 12, 16, 20, 24, 28, 32, 36 and 40 for patients entering from study SGT-54-01 or study SGT-54-02 and for new patients at: Weeks 4, 8, 12, 16, 20, 24, 28, 32, 36, 40, 44, 48 and 52. Study product weight will be documented) prior to dispensing and after return of each pump per flow chart ([Section 13.9](#) and [Section 13.10](#)).

Each Patient will be instructed on the importance of returning his or her study product at each designated visit. If a Patient does not return his or her study product, he or she will be instructed to return it at the next visit.

The study coordinator will question the patient on history of study product use since the last visit and will record any missed doses (as recorded on the patient diary) in both the source documents and the appropriate eCRF. A patient who deviates significantly from the prescribed dosage will be counseled.

Study product should be stored at room temperature 20 to 25°C (68 to 77°F). Excursions permitted between 15 to 30°C (59 to 86°F). Do not freeze or refrigerate the product.

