8.1.3 Visit Windowing

For subjects receiving S5G4T-1 in 54-01/54-02, data from 54-01/54-02 will be included in summaries of 54-07. For subjects receiving vehicle in 54-01/54-02, baseline values will be sourced from 54-01/54-02 and data from follow-up visits of 54-07 will be used in summaries. The table below details the analysis visits to be summarized and the associated visits from 54-01/54-02 or 54-07 which will be sourced for each type of subject.

Analysis Visits for Efficacy and Safety Assessments

Analysis Visit	Subjects Receiving S5G4T-1 in 54-01/54-02	Subjects Receiving vehicle in 54-01/54-02
Week 4	54-01/02 - Week 4	54-07 - Week 4
Week 8	54-01/02 - Week 8	54-07 - Week 8
Week 12	54-01/02 - Week 12	54-07 - Week 12
Week 16	54-07 - Week 4	54-07 - Week 16
Week 20	54-07 - Week 8	54-07 - Week 20
Week 24	54-07 - Week 12	54-07 - Week 24
Week 28	54-07 - Week 16	54-07 - Week 28
Week 32	54-07 - Week 20	54-07 - Week 32
Week 36	54-07 - Week 24	54-07 - Week 36
Week 40	54-07 - Week 28	54-07 - Week 40
Week 44	54-07 - Week 32	Not available
Week 48	54-07 - Week 36	Not available
Week 52	54-07 - Week 40	Not available

Data from 54-07 will be mapped to the appropriate analysis visit described above based on nominal visit indications. Data from Early Termination (ET) and unscheduled visits will be determined using analysis visit windows. The analysis visit windows for ET and unscheduled visits are presented in the following table.

SGT-54-07 Analysis Visit Windows for Efficacy and Safety Assessments

Nominal Visit	Target Study Day¹	Window (Days)
Week 4	29	22 to 42
Week 8	57	43 to 70
Week 12	85	71 to 98
Week 16	113	99 to 126
Week 20	141	127 to 154
Week 24	169	155 to 182
Week 28	197	183 to 210
Week 32	225	211 to 238
Week 36	253	239 to 266
Week 40	281	267 to 294
Week 44	309	295 to 322
Week 48	337	323 to 350
Week 52	365	351 to 378

¹ Number of days since nominal Baseline visit of 54-07

Data collected at ET and unscheduled visits prior to study day 22 will not be analyzed. Data collected at ET and unscheduled visits after study day 378 will not be included in analyses.

The definition for the study day included in each study window is defined as below:

Study Day prior to Day 1 = Visit Date – Day 1 Date

Study Day on or after Day 1 = Visit Date – Day 1 Date + 1

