8.9.2 Adverse Events

AEs from 54-01/02 will be included in the analysis for 54-07. All AEs that were reported as ongoing in 54-01/02 will be added into the CRF for 54-07, while AEs reported as recovered/resolved will be pulled forward programmatically into 54-07.

AEs occurring during the study will be recorded and classified on the basis of MedDRA terminology. Descriptions of AEs will include the date of onset, the date the AE ended, the severity of the AE, the relationship to study product, the action taken regarding study product usage, the action taken to treat the AE, and the outcome. All reported treatment-emergent AEs (TEAEs) will be summarized by the number of patients reporting AEs, system organ class, severity, seriousness, and relationship to study product. TEAEs are those AEs with an onset on or after the date of the first study product application. For AEs recorded in the 54-07 study if the AE is not indicated as prior to first application on the CRF then it will be considered a TEAE. AEs from 54-01/02 for subjects who received S5G4T-1 in 54-01 or 54-02 will be considered a TEAE if they were considered at TEAE in the 54-01/02 study. AEs (including ongoing) from 54-01/02 study for subjects who received vehicle in 54-01 or 54-02 will be considered pre-treatment.

AEs will be summarized by period (and total) and by severity. Each patient will be counted only once within a SOC or a Preferred Term by using the AEs with the highest severity within each category.

AEs will be summarized by period (and total) and by relationship to study product. Each patient will be counted only once within a system organ class or a preferred term by using the AEs with the greatest relationship within each category.

If relationship to study drug is reported as definitely, probably, or possible, then this is defined as related. If relationship to study drug is reported as unlikely or not related, then this is defined as unrelated.

TEAEs will be summarized in total as well as by the following periods based on time of onset in relation to date of first application of S5G4T-1, based on the definitions below. Start dates will be imputed as described in Section 8.1.5.2.

- 0-12 Weeks $0 \leq \text{onset day} \leq 85$
- >12-28 Weeks $86 \leq \text{onset day} \leq 197$
- >28-52 Weeks $198 \leq \text{onset day} \leq 365$
- >52 Weeks $\text{onset day} \geq 366$

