1 - Almost Clear	xx (xx.x%)	xx (xx.x%)	xx (xx.x%)
2 - Mild	xx (xx.x%)	xx (xx.x%)	xx (xx.x%)
3 - Moderate	xx (xx.x%)	xx (xx.x%)	xx (xx.x%)
4 - Severe	xx (xx.x%)	xx (xx.x%)	xx (xx.x%)
Achieving Clear or Almost Clear			
Success	xx (xx.x%)	xx (xx.x%)	xx (xx.x%)
Failure	xx (xx.x%)	xx (xx.x%)	xx (xx.x%)

^a Baseline is defined as the baseline value from SGT-54-01/SGT-54-02.

^b Table summaries based on nominal visit Week 40/ET from SGT-54-07.

SOURCE: USERNAME\SPONSOR\PROJECT\JOBNAME (DATE,TIME)

Table 14.2.1.2: Summary of Investigator Global Assessment at Each Evaluation
(Safety Population)
(Page 1 of 7)

Investigator Global Assessment	SGT-54-01/SGT-54-02	SGT-54-01/SG-54-02	SGT-54-07
	Vehicle Cream (N=xxx)	E-BPO 5% Cream (N=xxx)	E-BPO 5% Cream (N=xxx)
Baseline^a			
n	xx	xx	xx
0 - Clear	xx (xx.x%)	xx (xx.x%)	xx (xx.x%)
1 - Almost Clear	xx (xx.x%)	xx (xx.x%)	xx (xx.x%)
2 - Mild	xx (xx.x%)	xx (xx.x%)	xx (xx.x%)
3 - Moderate	xx (xx.x%)	xx (xx.x%)	xx (xx.x%)
4 - Severe	xx (xx.x%)	xx (xx.x%)	xx (xx.x%)
Week 4^b			
n	xx	xx	xx
0 - Clear	xx (xx.x%)	xx (xx.x%)	xx (xx.x%)
1 - Almost Clear	xx (xx.x%)	xx (xx.x%)	xx (xx.x%)
2 - Mild	xx (xx.x%)	xx (xx.x%)	xx (xx.x%)
3 - Moderate	xx (xx.x%)	xx (xx.x%)	xx (xx.x%)
4 - Severe	xx (xx.x%)	xx (xx.x%)	xx (xx.x%)
Achieving Clear or Almost Clear			
Success	xx (xx.x%)	xx (xx.x%)	xx (xx.x%)
Failure	xx (xx.x%)	xx (xx.x%)	xx (xx.x%)

^a Baseline is defined as the baseline value from SGT-54-01/SGT-54-02.

^b Table summaries based analysis visits, representing time from first dose of E-BPO 5% Cream.

SOURCE: USERNAME\SPONSOR\PROJECT\JOBNAME (DATE,TIME)

Table 14.2.1.2: Summary of Investigator Global Assessment at Each Evaluation
(Safety Population)
(Page 2 of 7)

Investigator Global Assessment	SGT-54-01/SGT-54-02	SGT-54-01/SG-54-02	SGT-54-07
	Vehicle Cream (N=xxx)	E-BPO 5% Cream (N=xxx)	E-BPO 5% Cream (N=xxx)
Week 8^b			
n	xx	xx	xx
0 - Clear	xx (xx.x%)	xx (xx.x%)	xx (xx.x%)
1 - Almost Clear	xx (xx.x%)	xx (xx.x%)	xx (xx.x%)
2 - Mild	xx (xx.x%)	xx (xx.x%)	xx (xx.x%)
3 - Moderate	xx (xx.x%)	xx (xx.x%)	xx (xx.x%)
4 - Severe	xx (xx.x%)	xx (xx.x%)	xx (xx.x%)
 Achieving Clear or Almost Clear			
Success	xx (xx.x%)	xx (xx.x%)	xx (xx.x%)
Failure	xx (xx.x%)	xx (xx.x%)	xx (xx.x%)
 Week 12^b			
n	xx	xx	xx
0 - Clear	xx (xx.x%)	xx (xx.x%)	xx (xx.x%)
1 - Almost Clear	xx (xx.x%)	xx (xx.x%)	xx (xx.x%)
2 - Mild	xx (xx.x%)	xx (xx.x%)	xx (xx.x%)
3 - Moderate	xx (xx.x%)	xx (xx.x%)	xx (xx.x%)
4 - Severe	xx (xx.x%)	xx (xx.x%)	xx (xx.x%)

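### By-visit tables labelled as time from first E-BPO dose count late-starting vehicle rollovers from the 54-07 Baseline visit

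*SAP*

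**What the plan says.** **The label.** Footnote b in SAP Section 12 reads "Table summaries based analysis visits, representing time from first dose of E-BPO 5% Cream". It stands on Tables 14.2.1.2 (IGA), 14.2.2.2 (RosaQoL), 14.2.3 (erythema), 14.2.4 (telangiectasia), 14.3.1.1 (cutaneous safety and tolerability) and the vital signs table.

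**The mapping.** SAP 8.1.3 states for patients who had vehicle in 54-01/54-02 that "data from follow-up visits of 54-07 will be used in summaries". Its table sends their 54-07 Week 4 to analysis Week 4, Week 8 to Week 8, and so on to Week 40. Scheduled visits follow the nominal label: "Data from 54-07 will be mapped to the appropriate analysis visit described above based on nominal visit indications". The windows for early termination and unscheduled visits are defined by "Number of days since nominal Baseline visit of 54-07". Neither rule mentions first application, and neither removes visits that precede it.

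**Entry and dispensing.** The Protocol Synopsis says that for rollovers "clinical exclusion criteria (IGA grade or lesion count) will not limit the enrollment for the study". Protocol 14.1 says that at IGA 0 or 1 "the patient will not be dispensed the study product". Protocol 17.4 includes the first visit in this rule: "Study product will be dispensed according to Investigator Global Assessment at: Baseline", followed by the later weeks.

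**Population and AE clock.** The Safety Population (SAP 8.4.1) needs one confirmed S5G4T-1 dose, at any time, plus an assessment. SAP 8.9.2 groups TEAEs by "periods based on time of onset in relation to date of first application of S5G4T-1".

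**The concern.** The footnote and the mapping agree only if a vehicle rollover's first S5G4T-1 dose falls at the 54-07 Baseline. A vehicle patient who enters clear or almost clear may go undosed until a later visit shows IGA 2 or more. The first dose brings that patient into the Safety Population together with all earlier 54-07 visits.

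Dryness, scaling, itching and burning/stinging are stated safety endpoints. For these patients, scores from skin never exposed to S5G4T-1 would sit in the early rows, and reactions in the first weeks of use would sit in later rows. The TEAE tables run from first application, so one report would place the same patient-day at two different exposure times.

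**Working it through.** **1. The plan's own figures.** With Day 1 = 54-07 Baseline, target day = 7 × week + 1. This gives 29, 57, 85, 113, 141, 169, 197, 225, 253, 281, 309, 337 and 365. All 13 target days in SAP 8.1.3 match, so the tabulated clock is the 54-07 Baseline clock.

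**2. The shift for a late starter.** Take a vehicle rollover first dosed at the 54-07 Week k visit, applying product that day, with all visits on target. First-dose day d0 = 7k + 1; exposure day = study day − d0 + 1. A scheduled visit at or before Week k is pre-exposure, because the IGA is scored before the product is dispensed. With dispensing only at scheduled visits, every pre-exposure visit except the last is IGA 0/1, and the last is IGA 2 or more.

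| First dose | d0 | Pre-exposure analysis visits | IGA 0/1 | IGA 2 or more | Weeks since first dose in row Week 40 (40 − k) |
|---|---|---|---|---|---|
| Baseline | 1 | 0 | 0 | 0 | 40 |
| Week 4 | 29 | 1 | 0 | 1 | 36 |
| Week 8 | 57 | 2 | 1 | 1 | 32 |
| Week 12 | 85 | 3 | 2 | 1 | 28 |
| Week 24 | 169 | 6 | 5 | 1 | 16 |
| Week 36 | 253 | 9 of 10 | 8 | 1 | 4 |

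**3. The two clocks side by side.** First dose at Week 12, visit on Day 113: the by-visit tables show Week 16. Exposure day = 113 − 85 + 1 = 29. SAP 8.9.2 puts onset days up to 85 in the 0-12 Weeks period, so an AE that day is counted there.

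**4. Direction for IGA success.** From the table, a Week 4 start adds one pre-exposure failure and no success. A Week 8 start adds one of each. Later starts add mostly successes.

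**5. Number of patients.** The documents give about 700 enrolled, but not the vehicle share, the share at IGA 0/1 on entry, or the share dosed later. Assumptions: vehicle 33-50% of 700 (700 × 0.33 = 231; 700 × 0.50 = 350); IGA 0/1 at entry, r = 10-30%; later dosed, q = 25-75%.

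- Low: 231 × 0.10 × 0.25 = 5.8, about 6.
- High: 350 × 0.30 × 0.75 = 78.75, about 79.

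As a share of vehicle rollovers in the Safety Population, if all others are dosed: rq / (1 − r(1 − q)).

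- Low: 0.025 / 0.925 = 2.7%.
- High: 0.225 / 0.925 = 24.3%.

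**The case against.** **Some passages put the first dose at Baseline.** Protocol Section 11 and SAP 6.1 say qualified rollovers are given product at Baseline, and Protocol 13.12 lists dispensing there without condition. On that reading mapping and footnote agree. This conflict is real and belongs with the finding, but it does not remove the problem. Protocol 17.4 and footnote 9 of the Protocol 5.2 flow chart tie Baseline dispensing to IGA. SAP 8.8.2 expects patients who are clear or almost clear in 54-07 to have been told not to dose, and SAP 8.9.1 counts applications missed on instruction. Holding a pump would therefore not establish a first dose.

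**The contamination is contained.** This stands. The affected efficacy and tolerability tables show prior-vehicle and prior-E-BPO patients in separate columns, and the prior-E-BPO column is sound to within visit windows. Exposure in SAP 8.9.1 runs from the first documented S5G4T-1 dose, and TEAE periods from first application. All summaries are descriptive, with no inferential test.

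**Off-drug visits are part of the design.** This also stands. Prior-E-BPO patients stop when clear too, so no correction makes Week k mean k weeks of drug. The footnote, however, claims time from first dose, and that can be made true.

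**Moving every visit to the first-dose clock would lose data.** This stands for RosaQoL and vital signs. For a first dose at Week 8, RosaQoL at 54-07 Weeks 12, 24, 36 and 40 becomes Weeks 4, 16, 28 and 32. None of these is among the summary weeks in SAP 8.8.2.1 or the table shells. Vital signs, planned at Weeks 12, 24, 36 and 48, have the same difficulty.

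**Conclusion.** For vehicle rollovers who enter with IGA 0/1, are not dosed at Baseline and are dosed later, footnote b is wrong as written. Their pre-exposure visits appear in E-BPO rows, and their later visits overstate time since first dose by the length of the undosed interval. The number is about 6 to 79 patients under the assumptions above. None of the three shares comes from the documents, but SAP Section 10 says enrolment was complete, so the sponsor can count them. This should be fixed before database lock.

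Three stronger readings are not supported:

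- A reader might infer that every vehicle patient clear at entry contributes, which would be 23 (231 × 0.10) to 105 (350 × 0.30). Those never dosed fall outside the Safety Population and contribute nothing.
- A reader might infer that remission on vehicle inflates E-BPO success. The effect can go either way, since the visit that triggers a first dose at a scheduled visit is a failure, and SAP 7.1 says the study is not meant to assess efficacy.
- A reader might infer that the long-term safety results as a whole are distorted. The TEAE tables, exposure totals and prior-E-BPO column do not change.

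**What to change.** In SAP 8.1.3, for patients who had vehicle in 54-01/54-02:

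1. Leave visits on or before the date of first S5G4T-1 application out of the E-BPO by-visit summaries, and list them as pre-treatment. Baseline stays as defined in SAP 8.1.2.
2. For the four-weekly assessments (IGA, erythema, telangiectasia, dryness, scaling, itching, burning/stinging), assign late starters' remaining visits by days since first application. This means extending the tabulated windows, now limited to early termination and unscheduled visits, to this group's scheduled visits. Patients first dosed at Baseline keep their present mapping.
3. For RosaQoL and vital signs, keep nominal visits, reword footnote b to time from 54-07 Baseline for this group, and report the number not yet dosed at each visit.

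Separately, the passages on receiving or dispensing product at Baseline (Protocol 11 and 13.12, SAP 6.1) must be reconciled with the IGA-dependent ones (Protocol 5.2, 14.1 and 17.4, SAP 8.8.2). If every vehicle rollover turns out to have been dosed at Baseline, steps 1 and 2 change no result.

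The cost is SAP wording and one derivation, using a first-application date the SAP already needs for TEAE periods and concomitant medication. The downsides are a slightly smaller n at early visits and window-based rather than nominal mapping for late starters.
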